#### **5.3.5 Day 30 Follow Up**

Between 25 and 35 days after the last therapy session (target value = 30 days), the subject will return to the central study site for testing, including testing related to the primary study endpoint. The study site will call the subject 1-2 days before this visit, reminding him/her of the time and place of the visit. All testing during the Day 30 Follow Up Visit will be performed by one of the site's Assessment Therapists, who will remain blinded to treatment assignment. To further protect the blinding of the Assessing Therapist, subjects will be reminded not to discuss with the Assessment Therapist any details of their six weeks of therapy. The assessments to be performed include vital signs, FM Scale, Box & Blocks Test, modified Rankin Scale, and Stroke Impact Scale-Hand Subsection. Additionally, the Assessment Therapist will record adverse events (which includes study-related adverse events, serious adverse events, and interval medical history), document any new medications and will document the amount of any therapy (OT, PT, SLT) that the subject received outside of study procedures

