### 5.3.1 Screening Visit

The Screening Visit occurs 3 weeks to 35 weeks after the date of stroke onset. The study site will call the subject 1-2 days before the Screening Visit, reminding the patient of the time and place of the visit. Prior to signing informed consent, the subject will be given the opportunity to become familiar with the Box & Blocks kit, and will be given the option to test him/herself given that only those persons who can score at least 3 blocks in one minute will be potentially eligible.

All procedures at the Screening Visit will be performed by one of the site's certified Assessment Therapists; in selected cases and with prior approval from the overall study PI ([name]), a site may request to have a different member of the research team be trained, certified and approved for performing selected assessments. For a given patient, all assessments should be performed by the same Assessment Therapist, as reasonably possible, across the Screening, Baseline, Post-Therapy, and Day 30 Follow Up Visits.

The study will be explained to the subject, after which the subject will be asked to sign informed consent. Next, screening for eligibility will ensue, including medical history, Fugl-Meyer test, Visual Acuity, Box & Blocks test, Montreal Cognitive Assessment, the 3 rehabilitation exercise test examples (used to insure that the subject is able to successfully follow instructions), and the Geriatric Depression Scale (GDS). Other measurements at this visit will include the modified Ashworth Spasticity Scale of the wrist, the Nottingham Sensory Scale, blood pressure, weight, the modified Rankin Scale, the NIH Stroke Scale, and the Stroke Knowledge Exam. The amount of any therapy (OT, PT, SLT) that the subject received since the time of stroke onset and prior and concomitant medications will be documented. Note that the Screening Visit assessments, with the exception of the Fugl-Meyer test, may be completed thereafter up to and including at the Baseline Visit. This is not encouraged but it is recognized that this may be useful for selected patients.

Subjects deemed eligible at the end of Screening Visit will be given the time and date of the Baseline Visit.

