#### Assessments:

All subjects will undergo a brief set of assessments during the third supervised therapy session then again every 3 supervised sessions until the end of therapy. These assessments will record adverse events (which includes study-related adverse events, serious adverse events, and interval medical history), ascertain subject compliance with the unsupervised therapy sessions, document any new medications, and document the amount of any therapy (OT, PT, SLT) that the subject received outside of study procedures. At the end of supervised sessions 6 and 12, the subject will be briefly asked about any new interval medical history events. In addition, at the end of supervised session 3 and supervised session 18, the PACES, OPS scale, and Patient Satisfaction Questionnaire will each be completed. These brief assessments will be performed by the subject's Treatment Therapist.

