#### **5.3.4 Post-Therapy Visit**

Immediately after the end of therapy (1-6 days following last day of therapy, target value = 2 days), the subject will return to the central study site for testing. The study site will call the subject the day before this visit, reminding him/her of the time and place of the visit. All testing during the Post-Therapy Visit will be performed by one of the site's Assessment Therapists, who will remain blinded to treatment assignment. To further protect the blinding of the Assessing Therapist, subjects will be reminded not to discuss with the Assessment Therapist any details of their six weeks of therapy. The assessments to be performed include FM Scale, Box & Blocks Test, Stroke Knowledge Exam, and Stroke Impact Scale-Hand Subsection. Additionally, the Assessment Therapist will record adverse events (which includes study-related adverse events, serious adverse events, and interval medical history), document any new medications and will document the amount of any therapy (OT, PT, SLT) that the subject received outside of study procedures.

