## **6. MANAGEMENT OF ADVERSE EVENTS**

This study will collect adverse events deemed likely to have resulted from study procedures as well as serious adverse events (SAE). These will be submitted online through WebDCU™ and coded centrally using MedDRA. The severity of any study-related adverse events and any SAEs will be graded according to the Common Terminology Criteria for Adverse Events (CTCAE).

Adverse events will be reported per NIH StrokeNet Network SOP ADM12 Central Institutional Review Board (CIRB) Reporting. The Principal Investigator retains responsibility for reporting to the CIRB and the StrokeNet National Data Management Center (NDMC), which is housed in the Data Coordination Unit (DCU) in the Department of Public Health Sciences at the Medical University of South Carolina (MUSC) supports this reporting requirement. The Principal Investigator also remains responsible for all investigator duties stipulated under the NINDS Guidelines for Data and Safety Monitoring in Clinical Trials, last updated August 8, 2013. The Child Study Site Principal Investigators are responsible for reporting adverse events at their sites to the CIRB as detailed in SOP ADM12

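### At both outcome visits the blinded Fugl-Meyer rater also records study-related adverse events, which can reveal the treatment arm before the primary rating

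*Combined protocol and SAP*

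**What the plan says.** Section 5.3.5 covers the visit at which the primary endpoint is measured: "All testing during the Day 30 Follow Up Visit will be performed by one of the site's Assessment Therapists, who will remain blinded to treatment". Sections 5.3.4 and 5.3.5 both add that "subjects will be reminded not to discuss with the Assessment Therapist any details of their six weeks of therapy".

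Both sections then give the same therapist further tasks: "Additionally, the Assessment Therapist will record adverse events (which includes study-related adverse events, serious adverse events, and interval medical history"), plus new medications. That therapist also "will document the amount of any therapy (OT, PT, SLT) that the subject received outside of study procedures". The schedule in Section 5.3 marks the adverse event and non-study therapy forms at both visits.

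Section 6 defines what is collected: "This study will collect adverse events deemed likely to have resulted from study procedures as well as serious adverse events (SAE"). A non-serious event therefore enters the record only through a judgement that study procedures caused it.

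Section 5.3.1 states the rater preference: "all assessments should be performed by the same Assessment Therapist, as reasonably possible, across the Screening, Baseline, Post-Therapy, and Day 30 Follow Up Visits". During the six weeks of therapy the same kinds of items are collected by someone else; under Assessments in Section 5.3.3, "These brief assessments will be performed by the subject's Treatment Therapist".

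**The concern.** The two instructions at each outcome visit pull against each other. The subject is to keep quiet about the therapy, and the same listener must record problems that the therapy caused. A subject who describes such a problem fully may mention the home computer and its controllers, or the clinic sessions. A subject who follows the reminder strictly may leave the event unreported.

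The primary endpoint is a rater-scored scale in a trial whose subjects know their assignment, so a rater who learns the arm could let expectation enter the score. In a non-inferiority trial, a shift in favour of telerehabilitation makes a false claim more likely, and a shift the other way costs power.

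**Working it through.** **Whether the documents close the route**

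1. *Can recording a related event reveal the arm?* Yes, in some cases. Sections 5.3.3.1, 5.3.3.2 and 11.3 describe supervised sessions in the clinic plus a paper booklet at home for one arm, and a computer system with game-type devices and videoconferencing for the other.
2. *Is a form order set?* No. Neither Section 5.3.4 nor 5.3.5 says that the motor scores come before the safety questions.
3. *Would an order within each visit be enough?* No. With the same rater at Post-Therapy and 30 Day, anything heard after scoring at the first visit is known when the primary score is taken at the second. Post-Therapy is 1-6 days after the last session and the 30 Day visit is 25-35 days after it.
4. *Is the task given to someone else at these visits?* No. Section 5.3.1 lets a site request, with prior approval, another trained team member for selected assessments. That provision is optional and sits in the Screening Visit section.
5. *Is there a check that blinding held?* None is described.

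**What a shift would do to the test**

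Inputs from Section 8: SD 4.0, 62 per arm, margin 2.05, 80% power, and non-inferiority judged on the lower bound of the two-sided 95% interval (one-sided 2.5%).

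The plan's own figure first. Normal approximation with a true difference of 0: n per arm = 2 x 4.0² x (1.96 + 0.8416)² / 2.05² = 59.8, so 60. The t-based calculation gives 61. The planned 62 per arm has power 0.814 (normal) or 0.808 (t), so 124 is consistent with 80% power. Allowing for dropout, 124 / 0.80 = 155, as stated.

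Standard error of the difference: SE = 4.0 x sqrt(2/62) = 0.718.

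Let s be the net shift in the arm difference from rater expectation. If a share f of one arm's ratings moves by b points and the other arm's do not, s = f x b. The values of f and b are assumptions; the documents give neither.

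- Shift favouring telerehabilitation, true difference exactly -2.05: false non-inferiority rate = Φ(s/0.718 - 1.96).
- Shift against telerehabilitation, true difference 0: power = Φ((2.05 - s)/0.718 - 1.96).

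| Assumed f x b | s (points) | s as % of margin | False non-inferiority | Power under the opposite shift |
|---|---|---|---|---|
| none | 0 | 0 | 2.5% | 81.4% |
| 5% x 1 | 0.05 | 2.4% | 2.9% | 79.5% |
| 10% x 1 | 0.1 | 4.9% | 3.4% | 77.5% |
| 10% x 2, or 20% x 1 | 0.2 | 9.8% | 4.6% | 73.1% |
| 20% x 2 | 0.4 | 19.5% | 8.0% | 63.2% |

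**The case against.** The case against is substantial, and much of it stands.

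- **The mechanism is inferred.** The protocol says record and document, and the form wording is not shown. Section 6 does not say who judges relatedness, and Section 11.1 gives reporting and response to the site lead investigator. A rater could note a symptom and leave attribution to others.
- **Many disclosures would not identify the arm.** Both groups do 18 unsupervised sessions at home, so a sore shoulder from home exercise fits either.
- **There should be little to record.** The Treatment Therapist has already collected events at six points through supervised session 18, the 30 Day interval contains no study therapy, and Section 11.1 expects study-related and serious events to be very unlikely.
- **Other safeguards exist.** Besides the reminder, Assessment Therapists have no involvement with subjects during therapy (Section 5.3.3), the two kinds of therapist work in separate locations (Section 10) and may not swap roles (Section 11.1), and Fugl-Meyer recertification is required every 4 months (Section 11.2).
- **The outside-therapy form is a weak route.** It asks for an amount of therapy received outside the study, and it is also completed before randomization.

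These points reduce the likely size. They do not remove the conflict, because separate buildings, separate roles and scoring certification do not govern what a subject says in an interview that the protocol requires the rater to hold. The reminder is the only safeguard that reaches that interview, and it conflicts with the interview's purpose.

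A reader might infer that the blind will be broken, that assessor blinding is the trial's only protection, or that the result is tilted towards non-inferiority. The documents support none of these. They give no unblinding rate and no direction of bias, and they describe the safeguards listed above.

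**Conclusion.** The point holds as a limited, avoidable risk to the primary rating. The conflict between the reminder and the recording duty is in the text of both outcome visits, and the same-rater preference carries a Post-Therapy disclosure into the 30 Day score. That recording can reveal the arm is an inference from the definition of a collectable event and the visible difference between arms; how often it would do so cannot be worked out from the documents.

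The figures above are illustrations. The false-claim rates apply only at a true difference of exactly -2.05, and the power figures only at a true difference of 0. Since related events are expected to be very unlikely, the smaller shifts (0.05 to 0.1 points, giving 2.9% to 3.4%, or power of 79.5% to 77.5%) are the more plausible for this route alone. No change to sample size, endpoint or analysis follows. The change is worth making because it is cheap and protects the primary endpoint.

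**What to change.** At the Post-Therapy and 30 Day visits, have the study coordinator or the Treatment Therapist complete the adverse event, interval history, medication and outside-therapy forms, in a separate location or by phone so that Section 10's separation is respected. State that this happens only after the Assessment Therapist's scores for that visit have been entered, and that the Assessment Therapist does not see these forms from either visit. Sections 5.3.4 and 5.3.5 should be amended together, since changing the order within each visit would leave the carry-over from Post-Therapy untouched. A short record of any accidental unblinding, or of the rater's guess at assignment, would be a useful optional addition.

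The cost is protocol wording, a form-order rule, and coordinating a second existing staff member at each outcome visit. The Treatment Therapist already collects adverse events, medications and outside therapy six times during therapy. Both candidates will know the assignment (the coordinator helps deliver and remove the home system), so the amendment should also bar them from passing it to the rater.

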### **5. 4. Prohibited Therapy/Medication**

Subjects may continue all therapy outside of study procedures as long as this non-study therapy does not interfere with the subject's fulfillment of study therapy and testing. The amount of any such outside therapy will be recorded at regular intervals.

The study protocol does not permit application of Botox to arm, leg, or trunk until after the 30 Day Follow Up visit is completed.

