### 5.3. Data Collection Schedule

Case Report Form	Screening	Baseline	End of 3 Supervised Sessions	End of 6 Supervised Sessions	End of 9 Supervised Sessions	End of 12 Supervised Sessions	End of 15 Supervised Sessions	End of 18 Supervised Sessions	Post-therapy	30 Day Follow Up	End of Study
Obtain Informed Consent	X										
Eligibility criteria	X										
Medical History	X										
Arm Motor Fugl-Meyer Scale	X	X							X	X	
Box & Blocks Test	X								X	X	
Montreal Cognitive Assessment	X										
Geriatric Depression Scale	X										
modified Ashworth Spasticity Scale(wrist)	X										
Nottingham Sensory Scale	X										
Blood Pressure & Weight	X									X	
modified Rankin Scale	X									X	
NIH Stroke Scale	X										
Stroke Knowledge Exam	X								X		
Non-study rehabilitation therapy	X	X	X	X	X	X	X	X	X	X	
(Pre-Stroke) Handedness Inventory		X									
Prior and Concomitant Medications	X	X	X	X	X	X	X	X	X	X	
Stroke Impact Scale-Hand Subsection		X							X	X	
Physical Activity Enjoyment Scale (PACES)		X	X					X			
Optimization in Primary and Secondary Control Scale (OPS)		X	X					X			
Randomization		X									
Patient Satisfaction Questionnaire			X					X			
Adverse Events			X	X	X	X	X	X	X	X	
Therapy Compliance			X	X	X	X	X	X			
End-of-Study Form											X

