### 8.1 Analysis of populations:

Primary efficacy analyses will be conducted on the Intent-To-Treat (ITT) Population, defined as all subjects who are randomized. Sensitivity analyses for efficacy will also be conducted on the Per-Protocol Population, defined as all subjects who complete assigned activities for at least 40 minutes at 15 or more of the 18 supervised therapy sessions over a period of time extending no more than 8 weeks. In ITT analysis, for missing data such as due to subject lost to follow-up, multiple imputation using all available evaluation data will be utilized. No interim analysis is planned.

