#### Primary efficacy analysis:

The primary analysis of the  $\Delta_{FM}$  will be conducted using an analysis of covariance (ANCOVA) model, adjusting for days from stroke onset to randomization, FM score at Baseline Visit, age, and enrollment site. The lower bound of the 95% confidence interval for the difference in  $\Delta_{FM}$  between treatment groups will be used to assess comparable efficacy. If the lower bound of the 95% confidence interval for the difference in  $\Delta_{FM}$  between groups (i.e.,  $\Delta_{FM}$

for the telerehabilitation group -  $\Delta_{FM}$  for the in-clinic group) is greater than -2.05, then we would declare telerehabilitation to be non-inferior.

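### Outside therapy and post-randomisation Botox are recorded but have no planned use in the analysis, and the Per-Protocol set keeps subjects who received the prohibited Botox

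*Combined protocol and SAP*

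**What the plan says.** Section 5.4 allows outside therapy on one condition: "Subjects may continue all therapy outside of study procedures as long as this non-study therapy does not interfere" with study therapy and testing. It gives no maximum. It adds that "The amount of any such outside therapy will be recorded at regular intervals". It also names one forbidden treatment: "The study protocol does not permit application of Botox to arm, leg, or trunk until after the 30 Day Follow Up visit is completed".

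The schedule in section 5.3 has rows for "Non-study rehabilitation therapy" and "Prior and Concomitant Medications". Both are marked at all ten contacts from Screening through the 30 Day Follow Up. Sections 5.3.1 to 5.3.5 confirm that amounts of OT, PT and SLT and any new medications are documented.

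Section 8.1 makes ITT the primary population and uses the Per-Protocol set for sensitivity. That set is "defined as all subjects who complete assigned activities for at least 40 minutes at 15 or more of the 18 supervised therapy sessions", over no more than 8 weeks. The primary ANCOVA is run "adjusting for days from stroke onset to randomization, FM score at Baseline Visit, age, and enrollment site"; section 8.3 also lists stroke subtype as a covariate. Nothing in section 8 summarises outside therapy or Botox by arm, analyses either one, or says how either is to be treated.

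**The concern.** The trial asks whether telerehabilitation is non-inferior when the study therapy is matched, and section 2.1 takes it as established that more therapy improves outcome. What a subject actually receives is study therapy plus whatever is obtained elsewhere. Section 14.4 expects that enrollees will be having, or will already have had, other rehabilitation. Subjects know their assignment, so uptake of outside therapy after randomisation could differ between arms.

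If it does, the difference in Fugl-Meyer (FM) change mixes the effect of the assigned programme with the effect of unequal outside therapy. More in the telerehabilitation arm would push the result toward non-inferiority. More in the in-clinic arm would push against it and cost power. Neither planned analysis would show this, although the data would be in the database.

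The Per-Protocol gap is more direct. The protocol forbids one treatment up to the primary endpoint, yet the set meant to represent adherence to the protocol does not consider whether that treatment was given. In a non-inferiority trial the Per-Protocol result is read as a check on the ITT result, so its definition should reflect the protocol's own prohibition.

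**Working it through.** **1. Is either data item used?** Section by section:

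| Item | Collected | Covariate (8.3, primary efficacy analysis) | By-arm summary (8.2–8.5) | Per-Protocol rule (8.1) |
|---|---|---|---|---|
| Outside therapy | Yes, ten contacts | No | No | No |
| Botox after randomisation | Through the general medication form | No | No | No |

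Section 8.2 tabulates adverse events only. Section 8.5 compares compliance with study sessions between arms, but not outside therapy.

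**2. The plan's own sample size.** Inputs from Determination of sample size: margin 2.05, SD 4.0, 80% power, two-sided 95% interval. The true difference is taken as 0, which is an assumption because the text does not state it.

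- n per arm = 2 × 4.0² × (1.96 + 0.84)² / 2.05² ≈ 60; the t-based version gives 61. The plan states 62.
- Power at 62 per arm is 0.81.
- 124 / 0.80 = 155, as stated.

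The planned size reproduces closely. The standard error of the difference is 4.0 × √(2/62) = 0.718.

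**3. An illustrative size for an outside-therapy imbalance.** The documents give no amounts, so the imbalance is assumed.

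- Active study minutes: 36 sessions × (80 − 10) = 2,520.
- Expected telerehabilitation gain: 4.80 points. Crediting all of it to therapy minutes gives 4.80 / 2,520 × 100 = 0.19 points per 100 minutes. This is an upper bound in the sense that none of the gain is assigned to spontaneous recovery.
- Assumed imbalance: 30–60 min/week over the 6 planned weeks, or over the 8 weeks allowed in section 5.3.3.

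The last two columns use SE 0.718:
- False non-inferiority when telerehabilitation is truly worse by exactly 2.05 and the imbalance favours it: Φ(b/0.718 − 1.96).
- Power at true equality when the imbalance favours in-clinic: Φ((2.05 − b)/0.718 − 1.96).

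| Extra minutes | Shift b (points) | Share of 2.05 | False non-inferiority | Power at equality |
|---|---|---|---|---|
| 0 | 0 | 0% | 2.5% | 81% |
| 30 × 6 = 180 | 0.34 | 17% | 7% | 66% |
| 60 × 6 = 360 | 0.69 | 33% | 16% | 48% |
| 30 × 8 = 240 | 0.46 | 22% | 9% | 60% |
| 60 × 8 = 480 | 0.91 | 45% | 25% | 35% |

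Three weaknesses of the rate:
- It treats an average gain as a linear effect per minute.
- The 4.80 comes from a 28-day pilot but is divided by this trial's minutes. If the 6.85 points assumed for the in-clinic group were used instead, every shift would scale by 6.85/4.80 = 1.43.
- Outside OT and PT minutes are not all arm therapy.

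**4. Therapy shared equally by both arms.** If its effect adds the same amount in each arm, it cancels from the difference and false non-inferiority stays at 2.5%. Only a ceiling or sub-additive effect that shrinks the true difference matters. An assumed 10% shrinkage gives 4.7% and 30% gives 13.5%.

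**5. Botox.** Exclusion criterion 11 removes anyone with Botox in the preceding 6 months or expected before the 30 Day visit. What remains is unplanned use after randomisation. The documents give no rate or effect for it, so no size is computed.

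**The case against.** The strongest case against is that this is a modest reporting gap. Under ITT, permitted outside therapy is part of the strategy being compared. Therapy already under way at randomisation is balanced in expectation. Botox is largely screened out at entry. These points stand, and they are why the primary analysis should not change.

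Four stronger readings are tempting, and the documents do not support them:

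- **Telerehabilitation subjects will get more outside therapy because in-clinic subjects make 18 clinic visits.** Both arms have 36 sessions of 80 minutes, and the extra in-clinic burden is mainly travel. No section indicates which arm would receive more.
- **The imbalance should be counted up to the 30 Day visit.** Running 30–60 min/week over about 10.3 weeks would give 29–57% of the margin. But the visit-burden argument ends with therapy, since neither arm has study sessions afterwards. Hence the 6–8 week range above.
- **Heavy outside therapy in both arms by itself favours non-inferiority.** It does so only if effects are sub-additive or reach a ceiling.
- **The claim of matched dose goes unchecked.** The matching claim concerns study therapy, and section 8.5 compares compliance across all 36 sessions by arm. Only the outside dose is unexamined.

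Nor is outside therapy unlimited in the full sense: it has no stated cap, but it must not interfere with study therapy and testing. A later check would also be possible from the collected data; it is just not planned.

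**Conclusion.** The point holds in a limited form. Data on outside therapy and medications are collected through to the primary endpoint and have no planned use, and the Per-Protocol definition overlooks the one treatment that section 5.4 prohibits.

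Any bias could run in either direction. At an assumed 30–60 min/week imbalance during therapy, it is about 0.3–0.9 FM points, or 17–45% of the margin. That rests on an assumed imbalance and on crediting the whole expected 4.80-point gain to therapy minutes, so it shows that the question deserves a look and is not a forecast. The Botox gap probably concerns few subjects, but it is a plain omission from a stated rule and nearly free to correct. The change should be made; the validity of the ITT primary analysis does not depend on it.

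**What to change.** - **Section 8.1:** add to the Per-Protocol definition that subjects whose medication records show Botox to arm, leg or trunk between randomisation and the 30 Day visit are excluded. Confirm that the medication form captures date and body site, since no Botox-specific item is described.
- **Section 8:** report outside OT and PT amounts from randomisation to the 30 Day visit by arm, with the between-arm difference and its 95% CI. State that the non-inferiority result will be interpreted in light of that difference.

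An analysis restricted to subjects with little outside therapy is optional and supportive only. It selects on a post-randomisation variable that treatment may affect, and its cut-off would be a matter of choice. For the same reason, outside therapy should not be added to the primary ANCOVA.

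The cost is a slightly smaller Per-Protocol set, one more table and a few lines of SAP text, using data already scheduled for collection. Sample size, the ITT primary analysis and the clinical rules in section 5.4 are unchanged.
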